5.1.1.1 Timing of Dose Administration

Trial treatment should be administered on Day 1 of each cycle after all procedures/assessments have been completed as detailed in the STUDY CALENDAR (Section 10). Trial treatment may be administered up to 1 day before or 3 days after the scheduled Day 1 of each cycle due to administrative reasons.

All trial treatments will be administered on an outpatient basis.

In general, toxicities from previous cycles of treatment should have returned to Grade 0-1 before the next dose of study medication (see Section 6.1 for specific guidance). Pre-existing Grade 2 toxicities, which did not result in exclusion from the trial, (for example, liver transaminase abnormalities) should be stable.

Pembrolizumab 200 mg will be administered as a 30 minute IV infusion every 3 weeks. Every effort should be made to target infusion timing to be as close to 30 minutes as possible. However, given the variability of infusion pumps from site to site, a window of -5 minutes and +10 minutes is permitted (i.e., infusion time is 30 minutes: -5 min/+10 min).

The Pharmacy Manual contains specific instructions for the preparation of the pembrolizumab infusion fluid and administration of infusion solution.

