- Assess for potential bacterial infection, biliary obstruction, or occult gastrointestinal bleeding
- Repeat ALT, AST, bilirubin, ALP, INR, and CBC with differential
- Other laboratories or imaging studies as clinically indicated
- Consider liver biopsy if indicated by hepatologist

Hepatitis C-Infected Subjects (including subjects who previously achieved SVR 12)

- In addition to the above, measure HCV RNA viral load

Hepatitis B-infected Subjects

- HBV DNA, HBsAg, anti-HBs, HbeAg and anti-Hbe
- Subjects should be questioned about compliance with the use of anti-viral agents.

Permanent Discontinuation Criteria for Subjects with Non-overdose Hepatic ECIs

Therapy should also be permanently discontinued for any of the following:

- ALT >20×ULN
- CP score of ≥9 points
- Gastrointestinal bleeding suggestive of portal hypertension (e.g., esophageal or gastric varices)
- New onset of clinically detectable ascites that cannot be managed with appropriate treatment
- Encephalopathy
- Recurrence of a severe or life-threatening event, or of any of the laboratory abnormalities listed above, that are presumed to be immune-related
- Other subjects may be eligible for treatment interruption (and potential re-start) of pembrolizumab after discussion with the Sponsor.

Diagnosis and Management of Non-Overdose Hepatic ECIs

HCC subjects are at risk for a range of complications that can cause hepatic laboratory abnormalities with or without clinical decompensation. Those with a history of chronic HCV or HBV infection also have the potential to experience virologic flares. Immune-related hepatitis has been observed in ~1% of subjects who received pembrolizumab. The following section provides further guidance on the diagnosis and management of potential hepatic complications among HCC subjects.

a. Hepatitis B Flare

Hepatitis B flares are characterized by rapid elevations of ALT and AST to >5×ULN and/or >3× baseline. ALT elevation to ≥10×ULN is common. In the absence of hepatic decompensation, ALT/AST elevations are typically isolated (i.e., limited/no elevations of bilirubin/ALP). This is accompanied (or preceded) by a detectable rise in HBV viral DNA in serum. An episode of elevated transaminases without increase in HBV DNA is not attributable to a viral flare.

Among subjects with HBV, a flare should be considered if this pattern is observed and there is no evidence of an alternative etiology. Guidelines for subjects with a diagnosis of HBV flare are as follows:

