6.4 Radiation Therapy Toxicity Assessment During Therapy

Expected toxicities from SBRT are listed in Section 7.1.1.2. Patients will be assessed at least once during radiation therapy for toxicity. Radiation therapy will continue as planned as long as there is no grade 3 or 4 toxicity, bilirubin is <51 mmol/L, Child score is A5-6 and the treating physician recommends continuation. Otherwise, a delay in radiation therapy should occur with possible

continuation of radiation if it resolves. If there is evidence of rapid changes in liver function suggestive of developing toxicity, or if the investigator has concerns regarding the clinical status of the subject, a delay in radiation therapy should be considered even if the criteria below are not met.

If the patient discontinues radiation therapy prematurely, the patient may be considered for further pembrolizumab, if criteria for treatment (see Section 6.1) are met within the allowed time window, and at the discretion of the treating Investigator.

Table 9: Radiation Therapy Toxicity and Suggested Modification

Toxicity	Modification
Hematologic Toxicities	
Grade 1-2	Continue radiation
Grade 3	Hold radiation until \leq grade 2, then resume
Grade 4	Hold radiation 1 week and until \leq grade 2, then resume
Gastrointestinal Toxicities	
Grade 1-2	Continue radiation
Grade 3-4 diarrhea	Hold radiation until \leq grade 2, then resume
Grade 1-2 nausea or vomiting	Initiate anti-emetics prior to radiation and as needed and continue radiation
Grade 3 nausea or vomiting	Hold radiation until \leq grade 2, then resume with anti-emetics prior to radiation and as needed
Hepatic Dysfunction	
Bilirubin 22-51 umol/L	Continue radiation
Bilirubin > 51 umol/L	Hold radiation until bilirubin improves to ≤ 51 mmol/L; treat as per hepatic ECI (Section 6.2) Consider resuming radiation only if rapid improvement.
Grade 1-2 AST/ALT	Continue radiation
Among subjects with baseline ALT $< 2 \times$ ULN: ALT $\geq 5 \times$ ULN	Hold radiation until bilirubin improves to \leq grade 2; treat as per hepatic ECI (Section 6.2). Consider resuming radiation only if rapid improvement
Among subjects with baseline ALT $\geq 2 \times$ ULN: ALT $> 3 \times$ the baseline level	
Child-Pugh Score > 7	Hold radiation until improves to Child-Pugh Score ≤ 7
Other non-hematologic toxicities	
Grade 1-2	Continue radiation
Grade 3	Hold radiation until improves to \leq grade 2, then resume
Grade 4	Discontinue radiation

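### Table 9 ends the ALT-triggered radiation hold on a bilirubin result, so the release condition in that cell names the wrong test

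*Combined protocol and SAP*

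**What the plan says.** Section 6.4 governs toxicity during SBRT. Its text lets radiation proceed "as long as there is no grade 3 or 4 toxicity", subject also to limits on bilirubin and Child-Pugh score and to the treating physician's recommendation. Otherwise radiation is delayed, with possible "continuation of radiation if it resolves".

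Table 9 then lists modifications by toxicity. Under hepatic dysfunction:

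- Bilirubin above 51 umol/L has its own hold, released when bilirubin falls to 51 or below.
- The row labelled "Grade 1-2 AST/ALT" continues radiation.
- ALT of at least 5xULN (baseline below 2xULN) triggers a hold. So does ALT above three times baseline (baseline 2xULN or above), if the cell beside the first ALT row also covers the second. The instruction reads "Hold radiation until bilirubin improves to" at most "grade 2; treat as per hepatic ECI (Section 6.2). Consider resuming radiation only if rapid improvement".

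The words "Hold radiation until bilirubin improves to" occur twice in the table: once in the bilirubin row, where they belong, and once in the ALT cell.

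Section 6.2, to which the cell refers, says of hepatitis B and C flares without decompensation: "ALT/AST elevations are typically isolated (i.e., limited/no elevations of bilirubin/ALP").

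**The concern.** A hold rule has two parts: the finding that stops treatment and the finding that lets it restart. Here the first is ALT and the second is bilirubin. Neither ALT trigger mentions bilirubin, so asking bilirubin to improve has no meaning in a patient whose bilirubin never rose.

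The rest of the cell does not fill the gap. Rapid improvement is required before resumption is considered, but no test, level or time is attached to it. A site that applies the cell literally checks a value that does not measure the toxicity behind the hold, and must work out the ALT level from elsewhere in Section 6.4.

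The setting makes this worth getting right. Section 5.1.2.1 gives possible overlapping liver toxicity as a reason for tighter liver dose limits in the first 10 patients, and Section 7.1.1.2 puts non-classic radiation-induced liver disease, which includes raised liver enzymes, at about 25%. Fractions are 24 to 72 hours apart (Section 5.1.2), so restart decisions are made quickly.

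**Working it through.** The plan gives no figure to reproduce. The check compares trigger with release across Table 9, then follows one case through the rule.

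**1. Trigger against release.** These are the holds in Table 9 that carry a printed release condition:

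| Hold triggered by | Printed release | Test the release refers to |
|---|---|---|
| Hematologic grade 3 | grade 2 or less | same, implied |
| Hematologic grade 4 | one week, and grade 2 or less | same, implied |
| Diarrhea grade 3-4 | grade 2 or less | same, implied |
| Nausea or vomiting grade 3 | grade 2 or less | same, implied |
| Bilirubin above 51 umol/L | bilirubin 51 or less | same, named |
| ALT | bilirubin grade 2 or less | **different, named** |
| Child-Pugh above 7 | Child-Pugh 7 or less | same, named |
| Other non-hematologic grade 3 | grade 2 or less | same, implied |

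Count: 2 named + 5 implied + 1 mismatched = 8.

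**2. Does the condition restrict ALT?** Take an illustrative patient with baseline ALT at 1xULN and bilirubin at grade 2 or below throughout. ALT rises to 10xULN, a level that Section 6.2 describes as common in flares.

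- Trigger: 10 is at least 5, so radiation is held.
- Printed release: bilirubin at grade 2 or less. It is true on the day the hold starts and stays true whatever ALT does.
- Release with ALT in place of bilirubin: not met until ALT itself is at grade 2 or less.

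The printed condition therefore sets no ALT requirement in this patient. The case is realistic: entry bilirubin may not exceed 34 umol/L (Table 1), HBV and HCV patients are eligible (Sections 3.1.10 and 3.1.11), and Section 6.2 calls the isolated pattern typical.

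**3. What was intended?** Three features point to ALT at grade 2 or less.

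- The bilirubin rows use absolute limits, whereas the ALT cell uses a grade, as does the AST/ALT row just above it.
- That row continues radiation at grade 1-2.
- The Section 6.4 text makes the absence of grade 3 or 4 toxicity the condition for continuing.

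The near-identical wording of the bilirubin release suggests that it was carried over into the ALT cell.

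**4. Does the cross-reference supply an ALT rule for radiation?** No. Section 6.2 does use ALT recovery after viral flares (to normal or grade 1, or to baseline grade), but for restarting pembrolizumab.

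**5. Units.** The bilirubin row triggers in umol/L and releases in mmol/L, and the Section 6.4 text also uses mmol/L. These differ by a factor of 1,000. This is clerical and separate from the ALT error.

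**The case against.** The strongest reply is that the cell should not be read alone. The text above the table already bars continuation with grade 3 or 4 toxicity and makes restart depend on resolution. Grades come from CTCAE v4.0 (Section 7.1), so that condition can be measured, and with the grade 1-2 row it gives the ALT level. This stands in large part. It is why the intended level can be inferred, and it limits the defect to one cell. It does not make the cell correct: a specific instruction naming another test competes with the general text.

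A reader might go further and infer that the protocol sets no ALT limit on restarting radiation anywhere from 5xULN up to 20xULN, the level in the Section 6.2 list that opens "Therapy should also be permanently discontinued for any of the following". The documents do not support that. The Section 6.4 text still applies across that range. The 20xULN end also assumes that therapy in that list includes SBRT, which is not stated. The list closes by speaking of interrupting and restarting pembrolizumab.

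Other points limit the exposure:

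- Table 9 is titled as suggested modification, and the cell only allows resumption to be considered.
- These ALT levels are hepatic events of clinical interest under Section 6.2: pembrolizumab is held, the sponsor is told within 24 hours, and evaluation, including a hepatologist's opinion and repeat ALT, is due within 72 hours.
- SBRT should finish within 15 days, and 22 days or more is an unacceptable deviation (Section 5.1.2.6). Section 6.2 gives 3 to 5 weeks (21 to 35 days) for laboratory abnormalities in HCV flare or recurrence, so a hold that waited for ALT would often outlast the window.
- HBV must be controlled at entry (Section 3.1.10).

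These are good reasons to expect few affected patients, not reasons to leave the wrong test in the table.

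**Conclusion.** The point holds as an error in one operative safety instruction: the only explicit, measurable release condition in the ALT cell of Table 9 names bilirubin. That is 1 of 8 printed release conditions. The error is certain for the first ALT row. That it extends to the second is inferred from the layout, because the second row's cell is blank in the text as extracted.

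The conclusion about an isolated ALT rise assumes that bilirubin is at grade 2 or below when the hold starts. The documents adopt CTCAE v4.0 without printing its cut-offs, so no bilirubin value is attached to that grade here. The number of patients affected cannot be estimated from the documents.

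It would be wrong to conclude that the protocol as a whole permits irradiation at any ALT. Read with its own text and the grade 1-2 row, Section 6.4 points to ALT at grade 2 or less. The primary endpoint, analysis and sample size are untouched. The correction is worth making because it concerns a liver-safety restart rule and costs almost nothing.

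**What to change.** In the ALT cell of Table 9, replace the word bilirubin with ALT and leave the rest as it stands: hold until ALT is at grade 2 or less, manage as a hepatic event under Section 6.2, and consider resuming only with rapid improvement. Print the cell against both ALT rows.

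Keeping grade 2 for the second row is workable. Section 5.1.1.1 already provides for such patients: "Pre-existing Grade 2 toxicities, which did not result in exclusion from the trial, (for example, liver transaminase abnormalities) should be stable". The release would not require ALT to fall below a baseline grade of 2. A separate baseline-relative release for radiation is not needed to correct this error.

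As a clerical change, alter mmol/L to umol/L for bilirubin in the Section 6.4 text and in the release cell of the bilirubin row.

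The cost is one word in one cell, printing that cell against the second row, and two unit corrections. Nothing changes in design, data collection or analysis.

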7. ADVERSE EVENTS: LIST AND REPORTING REQUIREMENTS

7.1 List of Adverse Events and Reporting Requirements

This study will utilize the CTCAE v4.0 for toxicity and Adverse Event reporting. A copy of the CTCAE v4.0 can be downloaded from the CTEP home page (<http://ctep.cancer.gov>). All appropriate treatment areas should have access to a copy of the CTCAE v4.0.

7.1.1 Expected Adverse Events and Protocol-Specific Expedited Adverse Event Reporting for Investigational Agent(s)

Adverse event (AE) monitoring and reporting is a routine part of every clinical trial. The following list of AEs and the characteristics of an observed AE will determine whether the event requires expedited reporting as an SAE in addition to routine reporting.

In addition, hospitalizations for routine procedures, protocol treatment, blood sampling, investigations and tissue biopsies are NOT considered SAE in this protocol.

7.1.1.1 Expected Adverse Events for Pembrolizumab

Refer to the current Pembrolizumab Investigator's Brochure for detailed information on adverse events.

Most Frequently Reported (Incidence ≥ 5%) Adverse Events Presented by decreasing Frequency and Considered Drug-Related by the Investigator in Participants Treated with Pembrolizumab

Likely (10-30%)

- Fatigue
- Pruritis
- Arthralgia
- Nausea
- Diarrhea
- Rash or itch

Less likely (<10%)

- Decreased appetite
- Asthenia
- Vitiligo
- Fever
- Hypothyroidism
- Myalgia
- Infusion reaction
- Hyperthyroidism

Rare (1% or less)

- Pituitary disorders
- Autoimmune hepatitis
- Myositis
- Autoimmune nephritis
- Pericarditis
- Pancreatitis
- Diabetes Mellitus
- Uveitis
- Hypoadrenalinism
- Myocarditis
- Myasthenia
- Sarcoidosis
- Encephalitis
- Stephen-Johnson Syndrome and Toxic Epidermal Necrolysis
- Myelitis

Most Frequently Reported (Incidence \geq 0.2%) Serious Adverse Events Presented by Decreasing Frequency and Considered Drug-Related by the Investigator in Participants Treated with Pembrolizumab

- Pneumonitis
- Colitis
- Diarrhea
- Pyrexia
- Hypopituitarism
- Pneumonia
- Adrenal insufficiency
- Hyponatraemia
- Dyspnoea
- Hyperthyroidism
- Type I Diabetes Mellitus
- Hypopituitarism
- Hypothyroidism
- Vomiting
- Aspartate aminotransferase increased
- Pericardial effusion
- Pleural effusion
- Alanine Aminotransferase increased
- Interstitial lung disease
- Autoimmune Hepatitis

7.1.1.2 Expected Adverse Events for SBRT

Very likely (80-90%)

- Fatigue (which generally resolves after radiation therapy is completed)
- Skin irritation, redness, itchiness, discomfort
- Temporary changes in blood work, without symptoms

Less likely (30%)

- Nausea, vomiting (during therapy) – more common if stomach or GI tract irradiated
- Diarrhea or sensitivity to food – more common if GI tract irradiated
- Gastritis, esophagitis, duodenitis, colitis – more common if relevant portion of the GI tract is irradiated
- Gastric, esophagus, small bowel or large bowel irritation/ulceration, bleeding, fistula, obstruction or changes in motility following therapy (may require medications or surgery) (<10% permanent changes)
- Chest wall pain, rib fracture (< 10%)

Less likely, but serious (<1-25%)

- Radiation-induced liver disease (RILD) (<5%). Classic RILD is a clinical diagnosis of anicteric ascites, hepatomegaly and elevation of ALP relative to other transaminases that may occur 2 weeks to 3 months following radiation to the liver.
- Non-classic RILD includes elevation of liver enzymes and/or any decline in liver function within 12 weeks from start of therapy (~25%). RILD can lead to liver failure that could lead to death. There is an increased risk of liver toxicity in patients with large tumors and in patients with pre-existing liver disease.
- Permanent thrombocytopenia (<1%); this may lead to bleeding
- Kidney injury (<1%); this may lead to changes on imaging and more rarely the need for medication.

7.2 Adverse Event Characteristics

- **CTCAE term (AE description) and grade:** The descriptions and grading scales found in the revised NCI Common Terminology Criteria for Adverse Events (CTCAE) v4.0 will be utilized for AE reporting. All appropriate treatment areas should have access to a copy of the CTCAE v4.0. A copy of the CTCAE v4.0 can be downloaded from the CTEP web site: http://ctep.cancer.gov/protocolDevelopment/electronic_applications/ctc.htm.
- **Attribution of the AE:**
 - Definite – The AE is *clearly related* to the study treatment.
 - Probable – The AE is *likely related* to the study treatment.
 - Possible – The AE *may be related* to the study treatment.
 - Unlikely – The AE is *doubtfully related* to the study treatment.
 - Unrelated – The AE is *clearly NOT related* to the study treatment.

Associated with the use of the treatment: There is a reasonable possibility that the experience may have been caused by the drug/biologic.

Life threatening adverse treatment experience: Any adverse drug/biologic experience that places the subject, in the view of the investigator, at immediate risk of death from the reaction as it occurred.

Serious adverse treatment experience: Any event is an AE occurring at any dose that results in any of the following outcomes:

- Death
- A life-threatening AE (The subject was, in the view of the Investigator, at immediate risk of death from the event as it occurred. It does not mean that the event, had it occurred in a more severe form, might have caused death).
- Hospitalization or prolongation of existing hospitalization (Complications that occur during hospitalization are AEs. If a complication prolongs hospitalization or fulfills any other serious criteria, the event is serious. Hospitalization for elective treatment of a pre-existing condition that did not worsen from baseline is not considered to be an AE).
- A persistent or significant disability/incapacity (A substantial disruption of a person's ability to conduct normal life functions. This definition is not intended to include experiences of relatively minor medical significance such as uncomplicated headache, nausea, vomiting, diarrhea, influenza, accidental trauma (i.e., sprained ankle) that may interfere or prevent everyday life functions but do not constitute a substantial disruption).
- A congenital anomaly/birth defect.
- Important medical events that may not result in death, be life-threatening, or require hospitalization may be considered serious when, based upon appropriate medical judgment, they may jeopardize the subject and may require medical or surgical intervention to prevent one of the outcomes listed in this definition (Examples include allergic bronchospasm requiring intensive treatment in an emergency room or at home, blood dyscrasias or convulsions that do not result in hospitalization or the development of drug dependency or drug abuse).

Any malignancy possibly related to cancer treatment (including AML/MDS) should be reported as an SAE. A second malignancy is one unrelated to the treatment of a prior malignancy (and is NOT a metastasis from the initial malignancy).

Events not considered to be serious adverse events are:

- hospitalizations for the routine treatment or monitoring of the studied indication, not associated with any deterioration in condition,
- treatment, which was elective or pre-planned, for a pre-existing condition that is unrelated to the indication under study and did not worsen,
- admission to a hospital or other institution for general care, not associated with any deterioration in condition, or
- treatment on an emergency, outpatient basis for an event not fulfilling any of the definitions of serious given above and not resulting in hospital admission.

Any SAE occurring after the subject has provided informed consent and until 4 weeks after the subject has stopped study participation must be reported. This includes the phase in which the study protocol interferes with the standard medical treatment given to a subject (e.g. treatment withdrawal during screening phase, change in treatment to a fixed dose of concomitant medication). Serious adverse events occurring more than 4 weeks after study discontinuation need only be reported if a relationship to pembrolizumab or SBRT is suspected.

Unexpected adverse treatment experience: Any adverse drug/biologic experience, the nature, frequency, or severity of which is not consistent with the product monograph, or not consistent with the risk information described above as a protocol-specific expected adverse event (see “Expected Adverse Events and Protocol-Specific Expedited Adverse Event Reporting Exclusions”, above).

Pembrolizumab Overdose: For purposes of this trial, an overdose of pembrolizumab will be defined as any dose of 1,000 mg or greater (≥ 5 times the indicated dose). No specific information is available on the treatment of overdose of pembrolizumab. Appropriate supportive treatment should be provided if clinically indicated. In the event of overdose, the subject should be observed closely for signs of toxicity. Appropriate supportive treatment should be provided if clinically indicated.

If an adverse event(s) is attributed to the overdose of a Merck product, the adverse event(s) is reported as a serious adverse event, even if no other seriousness criteria are met.

If a dose of Merck’s product meeting the protocol definition of overdose is taken without any associated clinical symptoms or abnormal laboratory results, the overdose is reported as a non-serious Event of Clinical Interest (ECI), using the terminology “accidental or intentional overdose without adverse effect.”

